#### 3.7 Safety Variables

The occurrence of safety events (SAE) between S1 in the NET-group/the first of three GP-consultations in the iTAU-group and T2, e.g. death, major depression or suicidality, hospitalization, and referral for psychiatric care, will be assessed systematically by the GP during the consultations. Any indications of SAE will be documented and reported to the PI and the data safety and management board (DSMB) (See section 13).

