#### 8.1.4 Safety analysis

Safety analyses will be conducted for SAE reported during the trial period. The frequency of events and the possible relationship to the treatment condition will be analysed descriptively. The number and percentage of patients experiencing each SAE will be presented for each treatment arm. The number and percentage of occurrences of each SAE will also be presented for each treatment arm. No formal statistical testing will be undertaken. Data quality including potential underreporting will be discussed.

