6.6 Safety Variables

The occurrence of safety events (SAE) between T0 and T2, e.g. death, major depression or suicidality, hospitalization, and referral for psychiatric care, will be assessed systematically by the GP during the consultations. Any indications of SAE will be documented and reported to the PI and the data safety and management board (DSMB) (See section 13).

7 Trial Design

7.1 General design issues:

This investigator-initiated study is designed as a prospective, randomized, multi-center, two-arm parallel-group, assessor-blinded, controlled, comparative effectiveness trial with a fixed sample design and a pragmatic attitude.

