10.2 Control intervention iTAU

Standard of care for post-ICU patients is characterized by low use of psychotropic medication and specialist care, or e.g., prescription of anti-depressive medication. Patients in the control group will receive usual care from their GP without any patient-individualised recommendations from the study protocol.

However, participating GPs will be instructed in evidence-based diagnosis and treatment for PTSD based on recommended standards (the S3-guideline; for example referral to psychiatric treatment, medication (e.g. anti-depressive), and general information about symptoms associated with PTSD). Based on the S3-guideline, the GP and the patient in the iTAU-group will conduct three medical consultations ("improved" treatment-as-usual, iTAU) between T0 and T1.

11 Prior and Concomitant care

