12.4 Control group

Between T0 and T1, the patient will be invited to consult her/his GP three times. These consultations should be performed as a face-to-face appointment. Further consultations may be conducted if needed. The content of the medical consultation is based on recommended standards (the S3-guideline; for example referral to psychiatric treatment, medication (e.g. anti-depressive), and general information about symptoms associated with PTSD).

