12.6.5 Follow-up period

The structured telephone interview “T1” for the primary comparison will be scheduled 6 months (+/-3 weeks) after T0.

The final evaluation will be performed during a structured telephone interview “T2” to be scheduled 12 months (+/-3 weeks) after T0. This will be defined as the regular end of trial on the patient-level. For patients who terminate the trial prematurely (treatment discontinuation), but without withdrawing her/his consent, this will be defined as the “dropout telephone interview”.

13 Safety Data Collection, Recording and Reporting

For this trial, the rules of safety data collection, recording, and reporting as known from pharmaceutical trials do not apply. Hence, we make no distinction between adverse and severe adverse events. All events are hereafter referred to as severe adverse events (SAE).

Serious adverse events (SAE) will be regularly monitored and investigated as of beginning of the intervention at S1 in the NET-group and the first of three GP-consultations in the iTAU-group until the end of trial at T2. The GP is the first point-of-contact during the intervention period and telephone interviewers at T1 and T2. If a patient cannot be reached via telephone at T1 and T2, the RCT will contact the respective GP for further information with regard to the patient's possible SAE-status. Any SAE will be reported to the Principal Investigator (PI) and the Data and Safety Monitoring Board (DSMB). The respective SAE-Form (see appendix) will be faxed by the GP or RTC immediately (within 24 hours the latest) to the PI. In addition to the reporting of the event to the PI and the DSMB, any SAE recorded during telephone interviews at T1 and T2 will immediately be entered into the study database via OpenClinica.

SAE include psychiatric emergency treatment, psychiatric inpatient treatment/hospitalization, significant deterioration of depression or PTSD-symptoms, acute suicidality and suicide.

In case of SAE, psychiatric back-up specialist of the following institutions are available to provide immediate support through the Depts. of Psychiatry affiliated to the ITC in Munich and to the RTCs in Berlin, Dresden, Hamburg and Tübingen (letter of declaration). These emergency back-up centers will be instructed accordingly.

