13.5.2 Reporting to the ethics committee

The DSMB will be informed on a regular basis. If a relationship between the intervention and the SAE cannot be ruled out, the PI will report the event to the ethics committee including following information:

- A full description of the event(s)
- Trial Site
- Severity
- Criteria for regarding the event as serious
- Description of specific symptoms
- Description of specific diagnosis.

All SAEs will be followed up and a follow-up report as well as a closing report will be sent to the ethics committee by the investigator.

14 Safety and Quality management

To reduce the risk of inefficient clinical management (i.e. exposition), GPs will be trained in accordance to GCP- and S3-Guidelines in their ability to care for patients with PTSD and to detect and deal with SAE appropriately. GPs will be trained to prompt immediate referral to specialist care (clinical pathway or trial back-up clinic) in case of SAE (i.e. of symptom deterioration). Clinical checklists will aid in detection of and reporting of deterioration in symptoms. Departments of Psychiatry in Munich, Berlin, Hamburg, Dresden and Tübingen have guaranteed to provide priority access to mental health services and psychiatric emergency treatment.

Similarly, telephone interviewers collecting data at T1 and T2 will be trained in detecting indications of SAE. All instructions and processes related to any interaction with the patient (face-

to-face or per telephone), to detection and handling of SAE and to handling of data will be described additionally accordingly as standard operating procedures (SOPs) for all staff involved.

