14.1 Data Safety and Monitoring Board

An independent Data and Safety Monitoring Board (DSMB) has been installed. The DSMB will monitor recruitment, feasibility, the integrity of the trial, safety of study participants, and will review recruitment rates and accumulating safety summaries on a regular basis; additional data may be requested during the conduct of the trial. A DSMB *Charter* will outline the roles and responsibilities of its members. The DSMB may recommend discontinuation of the trial or modification of the protocol for safety reasons at any time during the trial

Particular attention will be paid to the incidence of particular SAE reported during the trial period, including death, suicidal behaviour, “severe intrusions”, clinically significant intervention-related symptom deterioration, and referral to psychiatric care (e.g. psychiatric back-up centres located at the Departments of Psychiatry) or hospitalization.

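### Psychiatric referral is counted as an SAE although it is also named as control-arm care, so any overall SAE frequency by arm mixes delivered care with harm

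*SAP*

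**What the plan says.** **Where referral is an SAE.** SAP 3.7 describes the safety events as "e.g. death, major depression or suicidality, hospitalization, and referral for psychiatric care, will be assessed systematically by the GP during the consultations". In the iTAU arm the reporting window opens at the first of the three GP consultations. Protocol 6.6 has the same examples: "e.g. death, major depression or suicidality, hospitalization, and referral for psychiatric care". Protocol 14.1 directs the DSMB's particular attention to several SAEs, among them "and referral to psychiatric care (e.g. psychiatric back-up centres located at the Departments of Psychiatry) or hospitalization".

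**Where referral is control care.** Protocol 10.2 gives the content of the iTAU consultations by example: "for example referral to psychiatric treatment, medication (e.g. anti-depressive), and general information about symptoms associated with PTSD". Protocol 12.4 repeats it: "The content of the medical consultation is based on recommended standards (the S3-guideline; for example referral to psychiatric treatment". The iTAU schedule in protocol 12.6.4 says the same.

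**Where referral is not an SAE.** SAP 3.7 refers to section 13 for reporting. The SAP ends at section 11, so this can only be protocol section 13. Its opening text says: "SAE include psychiatric emergency treatment, psychiatric inpatient treatment/hospitalization, significant deterioration of depression or PTSD-symptoms, acute suicidality and suicide". The seriousness criteria in 13.1 do not name referral either. Section 13 also declares that all events are labelled SAE, so there is no lower category for a minor event.

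**Where referral is the response to an SAE.** The opening of protocol section 14 says: "GPs will be trained to prompt immediate referral to specialist care (clinical pathway or trial back-up clinic) in case of SAE".

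**What is analysed.** SAP 8.1.4 analyses the frequency of events descriptively and adds: "The number and percentage of patients experiencing each SAE will be presented for each treatment arm". Occurrences of each SAE are tabulated in the same way, without formal testing. The SAP synopsis says that all observed safety events will be summarised by arm.

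**The concern.** The same act, a GP referring a patient to psychiatric treatment, has three roles in these documents: part of the control intervention, an adverse outcome, and the required reaction to an adverse outcome. Nothing tells the GP or the analyst which role a given referral plays. The control GP makes the referral at the visits where he or she also screens for SAEs, and knows the treatment arm.

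The by-arm description of SAEs is the plan's only safety analysis, and checking for adverse effects of the intervention is a stated secondary objective. If an uneventful guideline referral enters that description as an SAE, an overall SAE percentage no longer measures harm alone. If a deterioration and the referral that follows are both entered, the count of occurrences no longer measures episodes.

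**Working it through.** **Step 1. Set the texts side by side.**

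| Place | Is psychiatric referral an SAE? |
|---|---|
| SAP 3.7; protocol 6.6 | Yes, a listed example |
| Protocol 14.1 (DSMB) | Yes, illustrated by the back-up centres |
| Protocol 13, opening text | Not named; psychiatric emergency and inpatient treatment are |
| Protocol 13.1 | Not named; there is an open category for other medically significant events |

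| Place | Role of referral in treatment |
|---|---|
| Protocol 10.2, 12.4, 12.6.4 | Example content of the iTAU consultations |
| Protocol 10, introduction | Part of the guideline training given to GPs in both arms |
| Protocol 14, opening text | Response to an SAE, no arm named |

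A planned referral at an iTAU consultation meets SAP 3.7 and is not excluded anywhere. The lists differ, and no rule says which one governs the tables in SAP 8.1.4.

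**Step 2. Occurrences.** Suppose a share f of deteriorations leads to referral and both are recorded. The occurrences per deterioration are then 1 + f. With f between 0 and 1 this runs from 1 (no double entry) to 2 (every episode entered twice). The documents give no value for f.

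**Step 3. Patients with any SAE.** The documents state no SAE or referral rate, so there is no figure of the plan to reproduce. What follows is an illustration under assumed rates.

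Inputs: 318 randomised (SAP 4.1) and 1:1 allocation (SAP 6), so about 318/2 = 159 per arm. Assumptions: other SAEs affect a share b of patients, the same in both arms; referral affects a share r; the two are independent.

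- Share with any SAE = 1 − (1 − b)(1 − r)
- Difference iTAU minus NET = (1 − b)(r_iTAU − r_NET)

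| b | r_iTAU | r_NET | Any SAE, iTAU | Any SAE, NET | Difference (points) | Patients (× 159) |
|---|---|---|---|---|---|---|
| 10% | 10% | 10% | 19.0% | 19.0% | 0 | 0 |
| 10% | 30% | 30% | 37.0% | 37.0% | 0 | 0 |
| 10% | 10% | 5% | 19.0% | 14.5% | +4.5 | +7.2 |
| 10% | 20% | 10% | 28.0% | 19.0% | +9.0 | +14.3 |
| 10% | 30% | 10% | 37.0% | 19.0% | +18.0 | +28.6 |
| 10% | 10% | 20% | 19.0% | 28.0% | −9.0 | −14.3 |
| 20% | 20% | 10% | 36.0% | 28.0% | +8.0 | +12.7 |
| 20% | 30% | 10% | 44.0% | 28.0% | +16.0 | +25.4 |

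With referral taken out, every row returns to b in both arms (10% against 10%, or 20% against 20%). The sign of the difference follows whichever arm refers more. With equal rates the difference is zero, but the percentages are still inflated: in the first row, from 10% to 19% in each arm.

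**The case against.** The strongest reply is that the planned table is by event type. SAP 8.1.4 presents each SAE separately, so referral may simply be one row, with deterioration and suicidality in their own rows. No pooled total is explicitly required. This stands in large part. It confines the distortion mainly to the overall frequency of events, which SAP 8.1.4 and the SAP synopsis still call for, and to any total built from the table. A referral row under an SAE heading also still presents delivered care as harm.

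Second, the lists are open, since both are given as examples or inclusions. Protocol 14.1 illustrates referral by the emergency back-up centres, which suggests that event-driven referral was meant. That is a reasonable guess at the intention, but no text says so, and SAP 3.7 carries no such limit.

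Third, referral is only an example of iTAU content, not a required step. This also stands, and it means the number of planned referrals cannot be predicted from the documents.

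A reader might go further and infer any of the following, which the documents do not support:

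- *NET will look safer.* GPs in both arms are trained in guideline referral. Protocol 10.2 describes standard care as having low use of specialist services. The NET arm adds seven calls, which under the SAP synopsis check PTSD symptoms and feed back to the GP; these could raise referral there.
- *A real excess of deterioration under NET would be hidden.* In a table by event type, deterioration keeps its own row.
- *Every iTAU referral would be classed as causally suspected and sent to the ethics committee.* The causality section within protocol 13.2 rests the decision on all accessible data. Only uncertain cases are handled as suspected.
- *Harmless referrals would outnumber genuine events.* No rate is given for either. The SAE definition also includes death and hospitalisation in a post-ICU population, for which the sample size section cites 18% six-month mortality in an earlier study.

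**Conclusion.** The point holds as a conflict of definitions that reaches the safety analysis. SAP 3.7 and protocol 6.6 and 14.1 count psychiatric referral as an SAE. Protocol 10.2, 12.4 and 12.6.4 name it as example control care. The section 13 lists omit it. No rule separates planned referral from referral after deterioration. Any overall SAE frequency by arm therefore mixes care with harm, and one episode can be counted twice.

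The size and direction of any between-arm distortion are unknown. Under the assumed rates shown, the any-SAE difference shifts by anything from −9 to +18 percentage points, and by zero when referral rates are equal. These figures assume 159 patients per arm, equal rates of other SAEs, and independence of referral from other SAEs. They show the mechanism and are not an estimate for this trial. The primary endpoint is not affected.

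**What to change.** 1. Reconcile the SAE lists in SAP 3.7 and protocol 6.6 and 14.1 with those in protocol section 13 and 13.1, and state which list governs SAP 8.1.4.
2. In SAP 8.1.4, report psychiatric referrals by arm in a table of their own. Where the record allows, split them into planned guideline care, response to deterioration, and reason not recorded.
3. Count each episode once: a deterioration and the referral that follows it are one occurrence.
4. Present any SAE total twice, with and without events whose only content is a referral. Classify those events before unblinding and blind to arm where the forms permit. SAP 8.5 already plans a blinded review of protocol violations, and this could be done alongside it.
5. Keep referral visible to the DSMB. It may signal deterioration, so deleting it from the watch list would lose information.

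The cost is a wording change, one extra descriptive table and a one-off review of forms on which referral is the only event. The limitation is that some forms may not give the reason for referral or may reveal the arm. The SAP should say how such forms are handled.

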# 4 Trial Design

#### General design:

This investigator-initiated study is designed as a prospective, randomized, multi-center, two-arm parallel-group, assessor-blinded, controlled, comparative effectiveness trial with a fixed sample design.

#### 4.1 Number of subjects

A total a number of N = 340 patients together with their treating GPs was calculated as the recruitment target. Recruitment was concluded on Dec. 31st 2022 with a total of N=318 randomized participants.

#### 4.2 Time Schedule

#### Per patient:

• duration of intervention, NET group: 18 weeks (6 weeks narrative session plus 12

weeks telephone monitoring)

• duration of intervention, iTAU group: 3 consultations with the GP between

randomization and T1

• duration of follow-up: 6 months

• total individual study duration: 12 months

#### Trial duration:

• Planned Start Date (Screening): 01.10.2017

• Planned Start Date – Enrollment (FPFV): 01.01.2018

• Planned End Date (LPLV): 31.12.2023 (including FUs)

The end of the clinical trial is defined by the last individual trial-specific examination during the last visit of the last patient to be part of the trial.

## 5 Trial Population, Eligibility Criteria, Recruitment

See study protocol.

# 6 Randomization and Blinding

Concealed randomization to both treatments (NET; iTAU) is performed with a 1:1 allocation ratio. The trial statistician will remain blinded to randomization codes throughout the course of the trial, i.e. until the study database has been finalised and locked for the final analyses after LPLV.

#### 7 Trial Procedures

#### 7.1 Methods of Assessment

The following section will give an overview and adequate explanations to the examinations and procedures (assessment instruments) that were performed in this trial. Screening instruments are described in section 8.7. Several clinical scores derived from patient questionnaires (mode of administration: paper-based self-administered or by telephone interview) were defined as primary and secondary outcomes.

#### 7.1.1 PDS-5 total severity score (PTDS symptoms)

The PDS-5 total severity score is derived from the 'Posttraumatic Stress Diagnostic Scale', a patient-reported questionnaire assessing the PTSD-related symptoms according to DSM-5 [validated German translation, Wittmann et al. Eur J Psychotraumatol. 2021]. Each of the 22 items refers to symptoms experienced in the past month only and is answered on a 5-point Likert scale ranging from 0 (not at all) to 4 (more than 5 times per week/ severe). This results in a total score with a range from 0 to 88 points. The PDS-5 total severity score has been found to have excellent psychometric properties and correlates with similar instruments for the diagnosis of posttraumatic stress, with high scores serving more severe PTSD symptoms (Foa et al., 2016). In this trial, the PDS-5 total severity score serves as key inclusion and exclusion criterion for the severity of PTSD symptoms at the beginning of the study prior to randomization.

#### 7.1.2 PHQ-9 (Depression)

Depressive symptoms experienced over the last 2 weeks will be assessed by means of the primary care validated Patient Health Questionnaire-9 (PHQ-9) (Kroenke & Spitzer, 2002). Each of the 9 items is scored from 0 'not at all' to 3 'nearly every day'. The PHQ-9 total sum score as a measure of depression severity ranges from 0 to 27, whereas a high score indicates severe impairment.

#### 7.1.3 OASIS (Anxiety)

The brief OASIS questionnaire is the only measure of anxiety severity and impairment applicable to multiple anxiety disorders that has been validated for use in primary care (Campbell-Sills et al., 2009) (Norman et al., 2011). The five items are inspired by the ICD-10 F40-43 criteria (for phobic and other anxiety disorders, obsessive-compulsive disorder, reaction to severe stress and adjustment disorders) and refer to all aspects of anxiety symptoms, including panic attacks, situational anxieties, worries, flashbacks, hypervigilance of startle, experienced over the past week.

There are five different response options for each item, which are coded 0–4 and summed to obtain the OASIS total score ranging from 0 (no anxiety) to 20 points. The five items ask about anxiety and fear, including frequency, intensity of symptoms, avoidance behaviour and impairments in daily life through these symptoms.

The OASIS-D is the German version of the validated original Anglo-American questionnaire, which was translated according to international standards for cross-cultural adaptation of self-report measures (Beaton DE, 2000) (Hiller TS, 2014) (Zlotnick et al., 2006)

#### 7.1.4 Disability (WHODAS 2.0 – short version)

The WHODAS 2.0 instrument is commonly used to assess disability (Üstün TB, Kostanjsek N, Chatterji S, & J, 2010). The WHODAS-2-short version contains 12 items on functioning and disability with a recall period of 30 days covering 6 domains: Cognition (2 items), Mobility (2 items), Self-care (2 items), Getting along with others (2 items), Life activities (2 items), and Participation in society (2 items). Response options go from 1 (no difficulty) to 5 (extreme difficulty or cannot do). WHODAS-2 scores are computed for each domain by adding the item responses and transforming them into a range from 0 to 100, with higher scores indicating higher levels of disability. A global sum-score across all domains are also computed. WHODAS 2.0 has good psychometric qualities, including good reliability and item-response characteristics, and its robust factor structure remains the same across cultures and in different patient populations (Üstün TB et al., 2010).

#### 7.1.5 PAM-Score (Thirteen-Item Patient Activation Measure)

As the promotion of active participation is one of the duties of the GP (Hibbard, Mahoney, Stockard, & Tusler, 2005), (Hollnagel & Malterud, 1995), the PAM measures the active participation of patients and the self-management of their state of health (Hibbard, Stockard, Mahoney, & Tusler, 2004) in form of a self-assessment. A short German version (PAM13) has been developed for use in clinical practice and research, that has good reliability and validity (Brenk-Franz et al., 2015) (Zill et al., 2013). The 13-item self-administered questionnaire assesses the knowledge of the patient regarding his/her health problems, the ability and the confidence to cope with these problems independently. Each item has four response categories with scores from 1 to 4: (1) strongly disagree, (2) disagree, (3) agree, and (4) strongly agree. The fourth item has an additional category with (5) not applicable. Evaluation is made by adding the raw values with a range of 13-52. For standardization of the gross total value, the sum-scale will be calibrated to a 0 to 100 metric.

